4.2.2.3 Antibiotic Use During the Trial

Non HS use:

Systemic antibiotics can be used for indications other than HS. A maximum of 4 weeks of systemic antibiotics are allowed from Week 0 - Week 12 for non-HS indications.

HS disease worsening (as defined above in [Section 4.2.2.2](#)):

After Week 12, systemic antibiotics may be used for disease worsening as per investigator discretion.

4.2.2.4 Analgesics Use During the Trial

Opiate analgesics (except synthetic opioids such as tramadol) are restricted for HS. It can be allowed for non-HS indications as per investigator discretion.

If a subject is on a non-opioid analgesic for HS and non-HS indication (e.g. osteoarthritis), the subject may continue the analgesic, provided the dose is stable from the 1368-0052 PoCC trial and is anticipated to remain stable throughout the study.

If a subject's pain (HS-related or non-HS-related) worsens after Visit 1, then non-opioid analgesic therapy may be initiated or increased.

Use of analgesics will be documented in the CRF.

4.2.2.5 Lesion Intervention

In the event that an acutely painful lesion occurs that requires immediate intervention, physicians will have the option to perform protocol-allowed interventions. Only two types of interventions are allowed: Intra-lesional steroid and Incision and Drainage (I&D). If I&D is performed, over the counter antiseptic wash can be used. Concomitant medications associated with the lesion intervention must be captured in the medical records. A total of two protocol-allowed interventions are permissible from W0 – W12. An intervention can maximally occur on two different lesions at the same time or on the same lesion at two different study visits. There are no restriction in the number of lesion interventions from W12 – EoT.

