4.2.2.2 Rescue Treatment

HS Disease worsening is defined as a 150% increase in AN count from baseline. Rescue medication is defined as the treatment for disease worsening, and includes systemic antibiotics or immunosuppressive biologics such as TNF-inhibitors. The sponsor will not provide/supply these treatment(s) to the sites. As per [Table 4.2.2.1: 1](#), immunosuppressive biologics are restricted during the entire trial. If a patient receives rescue treatment, the decision to maintain the patient on trial treatment is based on the investigator's clinical judgement.

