6.3 INTERCURRENT EVENTS

The expected intercurrent events (ICEs) of interest in this trial are:

- Use of rescue therapy (while still on treatment), as defined in [Section 5.4.3](#)
- Treatment discontinuation without restricted medication, flagged by medical review if occurring
- Treatment discontinuation with restricted medication, flagged by medical review if occurring

The strategies for handling intercurrent events in this trial are as follows:

Hybrid Strategy (EC-H): All intercurrent events except for the administration of rescue therapy will be handled using the treatment policy approach. Rescue therapy will be handled

using the hypothetical approach, under the scenario in which the intercurrent event would not occur. This will be used as the **primary strategy** of implementing the Estimand Concept (EC), allowing the effects of adherence, i.e., regardless of treatment discontinuation, but excluding the effects of rescue therapy.

No deaths are expected in this trial. In the unlikely event of a death occurring, it will be handled using a hypothetical approach for each strategy.

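### The visible plan does not name drainage and intra-lesional steroid injection as rescue or as intercurrent events, so lesion counts after them are used as observed and may overstate AN-based response

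*Protocol*

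**What the plan says.** - **Permitted procedures (Protocol 4.2.2.5).** There are two: intra-lesional steroid, and incision and drainage. The trigger is an acutely painful lesion needing immediate intervention. Early on, "A total of two protocol-allowed interventions are permissible from" Week 0 to Week 12. Later, "There are no restriction in the number of lesion interventions from W12" to end of treatment. On recording, the section says: "Concomitant medications associated with the lesion intervention must be captured in the medical records".
- **Rescue (Protocol 4.2.2.2).** "HS Disease worsening is defined as a 150% increase in AN count from baseline". Then: "Rescue medication is defined as the treatment for disease worsening, and includes systemic antibiotics or immunosuppressive biologics such as TNF-inhibitors". Lesion procedures are not mentioned.
- **Intercurrent events (SAP 6.3).** The first is "Use of rescue therapy (while still on treatment), as defined in" Section 5.4.3. The other two are treatment discontinuation with and without restricted medication. Section 5.4.3 is not in the public text.
- **Data set aside (SAP Table 6.4: 1 and 6.6.2).** The observed-case approach (OC) drops values after rescue. OC-NRI censors values after rescue and imputes non-response. Neither refers to any other treatment.
- **HiSCR (Protocol 5.1.1).** It requires at least a 50% fall in AN count with no increase in abscesses or draining fistulae, and is computed automatically from the counts.

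**The concern.** A drained abscess or an injected nodule is one of the units being counted. If it is absent from the next count because of the procedure, the change is recorded as improvement on spesolimab.

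Rescue does not obviously catch this. Its trigger is a 150% rise in the whole AN count, whereas one painful lesion is enough for an intervention. A patient can have several lesions treated without ever meeting the rescue definition.

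The secondary objective is efficacy at a lower dose than in the parent trial. Protocol 4.1.2 asks whether patients from the active arm sustain efficacy at half that dose. Procedures that keep counts down could hide loss of response, and with no concurrent control arm there is nothing against which to see it.

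**Working it through.** The plan gives no figure to reproduce: there is no sample size calculation and no hypothesis test (Protocol 7.1, 7.5). The check is a reading of the rules, then an illustration of size.

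**1. Do the visible rules reach these procedures?**

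| Rule | Covers | Names drainage or injection? |
|---|---|---|
| Protocol 4.2.2.2 | Treatment for disease worsening; antibiotics and biologics given as inclusions | No |
| SAP 6.3 | Rescue per 5.4.3; two kinds of discontinuation | No (5.4.3 not visible) |
| SAP Table 6.4: 1, 6.6.2 | Values after rescue | No |
| Protocol 5.1.1 | Automatic HiSCR from counts | No adjustment for treated lesions |

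SAP Section 4, which lists changes from the protocol's analysis, announces no wider rescue definition. On the visible text, counts after an intervention are used as observed.

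**2. Shift in percent AN change.** Let b be the baseline AN count (not given in the documents; assumed) and k the number of treated lesions no longer counted. The shift is 100 × k / b points.

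- b = 12, k = 1: 100/12 = 8.3 points
- b = 5, k = 1: 100/5 = 20 points
- b = 6, k = 2: 200/6 = 33.3 points

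**3. AN part of HiSCR.** It needs ceil(b/2) fewer lesions. If k are uncounted after a procedure, the remaining reduction needed is 100 × (ceil(b/2) − k)/b percent.

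| b | k = 0 | k = 1 | k = 2 |
|---|---|---|---|
| 5 | 60% | 40% | 20% |
| 6 | 50% | 33.3% | 16.7% |
| 10 | 50% | 40% | 30% |
| 12 | 50% | 41.7% | 33.3% |
| 20 | 50% | 45% | 40% |

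**4. Chance of meeting the AN part with no true change.** Assume the underlying count X is Poisson with mean b and that exactly k lesions go uncounted. The chance is P(X − k ≤ b/2).

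| b | k = 0 | k = 1 | k = 2 |
|---|---|---|---|
| 6 | 15.1% | 28.5% | 44.6% |
| 10 | 6.7% | 13.0% | 22.0% |
| 15 | 1.8% | 3.7% | 7.0% |

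This ignores HiSCR's abscess and fistula conditions, so it illustrates one component only.

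**5. Flare.** The definition requires an AN increase of at least 2 (Protocol 2.1.3). One uncounted lesion turns +2 into +1, and a borderline flare disappears. No baseline assumption is needed.

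**6. Trial level.** With about 45 patients, one reclassified patient moves a response rate by 100/45 = 2.2 points; five move it by 500/45 = 11.1 points.

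If treated lesions stay in the count, or if SAP 5.4.3 treats interventions as rescue, the unadjusted shift in steps 2 to 6 does not arise.

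**The case against.** **SAP 5.4.3 may already settle it.** The section is not visible, so its silence cannot be assumed. The protocol's wording that rescue *includes* two drug classes is not a closed list. SAP 7.2 summarises non-drug therapies excluding rescue, which makes most sense if some rescue is not a drug. This stands, and the point is conditional on it.

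**Nothing says a treated lesion leaves the count.** A reader might infer that these procedures remove lesions from the AN count and that each treated lesion is scored as drug response. The documents do not say so. Protocol 5.1.2 describes an abscess as containing pus, so a successfully drained one may no longer fit the description. For injected nodules, loss from the count is only plausible. The supported claim is that response may be overstated because no visible rule prevents it.

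**The affected endpoints are uncertain.** A reader might also infer that every lesion-based secondary endpoint is biased in the unlimited period. The endpoint weeks are redacted, so this is unproven. If they end at Week 12, the unlimited period reaches only the over-time displays in SAP Section 4, although counts continue to Week 98. The two early interventions would still fall inside the secondary window.

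**Observed values may be what the SAP intends.** SAP 6.3 applies treatment policy to every intercurrent event except rescue. That is a defensible main analysis, and it is why the remedy is a sensitivity analysis.

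**Draining a new lesion only returns the count to where it was.** This is true of some cases, but the count is still lower than it would have been without the procedure. After Week 38 counts are 12 weeks apart, so many interventions may not closely precede one.

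**Conclusion.** The concern holds as a conditional gap. Procedures on counted lesions are allowed throughout, without limit after Week 12, and no visible rule says how later counts are handled. Unless SAP 5.4.3 classes them as rescue, AN change, abscess count and elimination, HiSCR and IHS4 may look better than the drug effect, and flares may be masked. This applies from Week 0 to Week 12 and in the over-time displays afterwards.

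The size is 8 to 20 points of percent AN change per uncounted lesion. It rests on two assumptions that the documents do not settle: a baseline AN count of 5 to 12, and that the treated lesion is not counted at the next assessment. The frequency of interventions is unknown, so the effect on the trial's results cannot be estimated.

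Efficacy is exploratory and descriptive, and the primary endpoint is treatment-emergent adverse events, so no confirmatory conclusion is at risk. The check is worth making because it bears on whether response is sustained at the lower dose.

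**What to change.** 1. Confirm whether the rescue definition in SAP 5.4.3 covers drainage and intra-lesional steroid. If it does, say so in SAP 6.3; steps 2 and 3 are then not needed.
2. If it does not, add to SAP 6.3 and 6.6.2 a sensitivity analysis in which lesion-based values after a protocol-allowed intervention are handled as after rescue: excluded under OC, non-response under NRI. Under the NRI rule that bridges between two successful visits, the intervention should count as rescue.
3. Confirm that the intervention date is in the CRF. Protocol 4.2.2.5 asks only for associated medications in the medical records, whereas 4.2.2.4 asks for analgesics in the CRF.
4. Tabulate interventions per patient, separately for Week 0 to Week 12 and after Week 12.

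Keeping every treated lesion as present at all later visits is not recommended. It needs lesion-level tracking, while the flow charts list counts. It also accumulates: at a baseline of 6, four treated lesions leave at least 4/6 of the count, a maximum reduction of 33%, so HiSCR could never again be met.

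The cost is SAP wording and a data check; no clinical rule changes. Response rates in the sensitivity analysis will be lower, and some observed data are set aside. Because one early procedure makes a patient a non-responder from then on, the result should be read as a conservative bound beside the main analysis.

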4.2.2.6 Restrictions on Diet and Life Style

No specific restrictions on diet or life style of the patients are required.

4.2.2.7 Contraception Requirements

WOCBP (for the definition please refer to [Section 3.3.2](#)) must use highly effective methods of birth control per ICH M3 (R2) that result in a low failure rate of less than 1% per year when used consistently and correctly during the trial, and for a period of at least 16 weeks after the last study drug administration. A list of contraception methods meeting these criteria is also provided in the patient information.

Female Patients

Acceptable methods of birth control for this trial are:

- Combined (oestrogen and progestogen containing) hormonal birth control that prevents ovulation (oral, intravaginal, transdermal)
- Progestogen-only hormonal birth control that prevents ovulation (oral, injectable, implantable)
- Intrauterine device or intrauterine hormone-releasing system
- Bilateral tubal occlusion
- Vasectomised sexual partner with documented absence of sperm

Or

Patients must abstain from male-female sex. This is defined as being in line with the preferred and usual lifestyle of the patient. Periodic abstinence e.g. calendar, ovulation, symptothermal, post-ovulation methods; declaration of abstinence for the duration of exposure to study drug; and withdrawal are not acceptable.

Male Patients

Contraception of male trial participants and female partners of male trial participants are not required.

4.3 TREATMENT COMPLIANCE

Administration of the study medication will be done in the study centre under the supervision of the investigator or a designee. The measured plasma concentrations will provide additional confirmation of compliance.

5. ASSESSMENTS

All assessments are measured at the time points noted in the [Flow Chart](#) and preferably completed prior to study drug administration.

5.1 ASSESSMENT OF EFFICACY

5.1.1 Hidradenitis Suppurativa Clinical Response - HiSCR

The HiSCR is one of the most well-known and widely used outcome assessment in clinical trials. HiSCR is defined as at least a 50% reduction from baseline in the total AN count, with no increase in the abscess or draining fistula count. [\[R20-2976\]](#) HiSCR is calculated automatically by comparing the lesion count from baseline.

5.1.2 International Hidradenitis Suppurativa Severity Score System - IHS4

IHS4 is a valid, clinical scoring system for dynamic assessment of HS severity. Determining IHS4 requires counting nodules, abscesses and draining fistulae/sinus tracts making it straightforward to apply in clinical trials [\[R20-3045\]](#).

A nodule (inflammatory nodule) is a raised, three dimensional, round, infiltrated lesion with a diameter of >10 mm. An abscess is a tender but fluctuating mass with a diameter of >10 mm, surrounded by an erythematous area; the middle of an abscess contains pus. A draining tunnel is a raised, tender but fluctuating longitudinal mass of variable length and depth, ending at the skin surface, and sometimes oozing a fluid. Fistulae and sinuses are examples of tunnels.

5.1.3 Hidradenitis Suppurativa Physician Global Assessment - HS-PGA

This documents the physician's assessment of the patient's HS at a given time point. It scores patient disease severity as either clear or minimal or mild or moderate or severe or very severe, based on abscesses, draining fistulae, inflammatory nodule and non-inflammatory nodule.

5.1.4 Hidradenitis Suppurativa Area and Severity Index - HASI

HASI is modelled after the Psoriasis Activity and Severity Index (PASI). Four classic signs of HS-related inflammation (erythema, thickness, drainage, tenderness) are included. Each variable in HASI is scored on a Likert scale (0–3) for each predetermined body region. For BSA assessment, the number of palms (one palm indicated 1% of the patient's BSA) involved for each body region (head, right axilla, left axilla, anterior chest, back, anterior bathing trunk, posterior bathing trunk, other) is assessed. This is converted to a percentage of that region. An area score was assigned to each region using the PASI approach (0 = none, 1 = 1–9%, 2 = 10–29%, 3 = 30–49%, 4 = 50–69%, 5 = 70–89%, 6 = 90–100%). To calculate the regional HASI score, the sum of the four clinical variable scores is multiplied by the area score of each involved region. This value is then multiplied by the proportion of the BSA of that region, to give a regional HASI score. Regional HASI scores are added together to give the cumulative total HASI score (range 0–72).

5.1.5 Pain Numerical Rating Scale – Pain NRS

The Pain NRS is an endpoint for the assessment of HS-related pain severity for clinical trials with patients with HS. It is a unidimensional measure of pain intensity and can be administered monthly at the site. Response is given by an 11-point scale ranging from 0 to 10. The Pain NRS is completed by the patients during clinic visits. It will be used to assess the worst HS pain. Ratings will range from 0 (no HS pain) to 10 (HS pain as bad as one can imagine).

5.1.6 Dermatology Life Quality Index

The DLQI is a patient-administered, ten-question, quality of life questionnaire that covers six domains including symptoms and feelings, daily activities, leisure, work and school, personal relationships and treatment [R05-2548]. The DLQI has a one-week recall period. Response categories include “not relevant” (score of 0), “not at all” (score of 0), “a little” (score of 1), “a lot” (score of 2) and “very much” (score of 3). Question 7 is a “yes”/ “no” question where “yes” is scored as 3.

The DLQI will be analyzed under six headings as follows [R05-2548]:

Domain	Question Number	Score
Symptoms and feelings	Questions 1 and 2	Score maximum 6
Daily activities	Questions 3 and 4	Score maximum 6
Leisure	Questions 5 and 6	Score maximum 6
Work and school	Question 7	Score maximum 3
Personal Relationships	Questions 8 and 9	Score maximum 6
Treatment	Question 10	Score maximum 3

DLQI total score is calculated by summing the scores of each question resulting in a range of 0 to 30 where 0-1 = no effect on patient’s life, 2-5 = small effect, 6-10 = moderate effect, 11-20 = very large effect, and 21-30 = extremely large effect on patient’s life. The higher the score, the more the quality of life is impaired. If one question is left unanswered this is scored 0 and the total score is summed and expressed as usual out of a maximum of 30; for analysis by subscore only, the corresponding subscore is considered to be missing. If 2 or more questions are left unanswered (missing), DLQI total score is treated as missing. A 4-point change from baseline is considered a clinically important difference.

5.1.7 Hidradenitis Suppurativa Quality of Life – HiS-QoL

The HiS-QoL is a patient-administered, 17-item instrument to measure HS-specific quality of life in clinical trials with a 7-day recall period [R20-3156]. The 17-item HiS-QoL included four symptom items, eight activity-adaptation items and five psychosocial items. The item scores are summed to create a total ranging from 0 to 68, with higher scores indicating more

severe impact on HRQOL. The subscale scores range from 0 to 16 for symptoms, 0 to 20 for psychosocial and 0 to 32 for activities-adaptations.

5.1.8 FACIT-Fatigue Scale

The FACIT-Fatigue Scale is a 13-item questionnaire ([R10-6433], [R07-4311], [R16-0029]) that assesses self-reported fatigue and its impact upon daily activities and function. Answers are based on a 5-point Likert scale. Responses of “not at all,” “a little,” “somewhat”, “quite a bit,” and “very much” are available for each question, and correspond to scores of 0, 1, 2, 3, and 4, respectively (total score range: 0-52). A minimal clinically important difference of 3-4 points in change score has been reported [R16-0029]. The recall period for items is 7 days.

5.1.9 Patient Global Impression of Change - PGI-C

The PGI-C is a 1-item tool assessing the change of HS since the start of taking the study medication by 5-point Likert-type scale. The tool is required for anchoring of other instruments and endpoints.

5.1.10 Patient Global Impression of Severity - PGI-S

The PGI-S is a 1-item tool assessing the severity of HS over the last week by 4-point Likert-type Scale. The tool is required for anchoring of other instruments and endpoints.

5.2 ASSESSMENT OF SAFETY

5.2.1 Physical examination

A complete physical examination will be performed at the time points specified in the [Flow Chart](#). It includes at a minimum general appearance, neck, lungs, cardiovascular system, abdomen, extremities, and skin.

A targeted physical examination will be performed at the time points specified in the Flow Chart. It includes evaluation of organ systems associated with AE(s) symptoms or laboratory abnormalities.

Measurement of height and body weight will be performed at the time points specified in the Flow Chart.

The results must be included in the source documents available at the site.

5.2.2 Vital signs

This includes temperature, respiratory rate, systolic and diastolic blood pressure and pulse rate (electronically or by palpation count for 1 minute) in a seated position after 5 minutes of rest. The results must be included in the source documents available at the site. Measurement of vital signs should precede blood sampling to avoid the impact of blood sampling on the vital measurements. Additionally, vital signs will be measured approximately 10 min post-dose after s.c. administration and approximately 5 and 60 min. post-dose in case of i.v. study drug administration. Also at Visit 2 and Visit 3 additional measurements will be performed

approximately 60 minutes after s.c. study drug administration. Hypersensitivity reactions should be treated according to medical standards. Pre-medications for further injections might be considered and will be agreed on between investigator and the sponsor.

5.2.3 Safety laboratory parameters

Safety laboratory parameters to be assessed are listed in [Table 5.2.3.1](#). For the sampling time points please see the [Flow Chart](#).

All analyses will be performed by a central laboratory, the respective reference ranges will be provided in the ISF. Patients do not have to be fasted for the blood sampling for the safety laboratory. If blood sampling for central lab is not possible because central laboratory supplies are not available on time, safety lab analyses can be performed at a local laboratory. The results of the local lab tests must be reported to the investigator who ensures medical review and proper documentation in the eCRF.

Instructions regarding sample collection, sample handling/ processing and sample shipping are provided in the Laboratory Manual in the ISF. The central laboratory will send reports to the investigator. It is the responsibility of the investigator to evaluate the laboratory reports. Clinically relevant abnormal findings as judged by the investigator will be reported as adverse events (please refer to [Section 5.2.6](#)).

In case the criteria for hepatic injury are fulfilled, a number of additional measures will be performed (please see [Section 5.2.6.1](#) and the DILI Checklist provided in the ISF and/or the electronic data capture (eDC) system. The amount of blood taken from the patient concerned will be increased due to this additional sampling. The central laboratory will transfer the results of the analysis to the sponsor.

Table 5.2.3:1 Infection testing at Visit 1 and EoT visit

Category	Test Name
Infection Testing	Hepatitis B virus-DNA (quantitative) at Visit 1 and EoT Visit ¹ QuantiFERON®-TB-Gold Plus ^{2, 3, 4} Hepatitis B Surface Antigen (qualitative) ⁵ Hepatitis B core Antibody ⁵ Hepatitis C Antibodies (qualitative) ⁵ HIV-1, and HIV-2 Antibody (qualitative) ⁵ T-spot TB test

1. An HBV-DNA should be conducted if Hepatitis B core Antibody is positive and Hepatitis B Surface Antigen is negative. These evaluations should be conducted at Visit 1 and at the EoT visit.
2. There is the trial site option to perform a PPD skin test.
3. Patients with indeterminate QuantiFERON or invalid/borderline T-spot may be retested with IGRA (once) and if inconclusive should have a PPD skin test.
4. In patients with a previously (i.e., in the previous PoCC trial or in this ongoing extension trial) negative QuantiFERON®-TB test, the test should be repeated every 52 weeks, as long as the results are negative.
5. If determined as negative at Visit 1, then there is no need to retest at the EoT Visit.

Table 5.2.3:2 Safety laboratory tests

Category	Test Name
Haematology	Hematocrit (Hct) Hemoglobin (Hb) Glycosylated Hbc (HbA1c) (Only at baseline) Red Blood Cell Count/ Erythrocytes Reticulocyte Count White Blood Cells / Leukocytes Platelet Count/ Thrombocytes
Diff. Automatic	Neutrophils (relative and absolute count) Eosinophils (relative and absolute count) Basophils (relative and absolute count) Monocytes (relative and absolute count) Lymphocytes (relative and absolute count)
Diff. Manual (if Diff Automatic is abnormal)	Neutrophils, bands (Stabs) Neutrophils, polymorphonuclear (PMN) Eosinophils Basophils Monocytes Lymphocytes
Coagulation	Activated Partial Thromboplastin Time (aPTT) Prothrombin time (INR) Fibrinogen
Enzymes	AST (GOT) ALT (GPT) Alkaline Phosphatase (AP) Creatine Kinase (CK) CK-MB, only if CK is elevated Gamma-Glutamyl Transferase (GGT/γ-GT) Lactic Dehydrogenase (LDH) Amylase Lipase
Electrolytes	Calcium Sodium Potassium Chloride Bicarbonate

Category	Test Name
Substrates	Glucose BUN (blood urea nitrogen) Uric acid Creatinine ⁴ eGFR (estimated by CKD-EPI formula) (only at Visit 1) Bilirubin Total Bilirubin Direct (if total is elevated) Bilirubin Indirect (if total is elevated) Troponin (Reflex, in case of elevated CK) Protein, total Albumin C-Reactive Protein (CRP & hs-CRP) (high sensitivity) Cholesterol, total Triglycerides LDL-Cholesterol HDL-Cholesterol
Specific gamma-globulin quantification	IgE ¹ , IgG
Urine Pregnancy test (only for WOCBP)	Human Chorionic Gonadotropin in urine
Serum Pregnancy test (only for WOCBP if urine pregnancy test is positive)	Human Serum Chorionic Gonadotropin
Urinalysis (dipstick)	Urine Nitrite Urine Protein Urine Glucose Urine Ketone Urobilinogen Urine Bilirubin Urine RBC/ Erythrocytes / Blood Urine WBC/ Leukocytes Urine pH Specific gravity

Category	Test Name
Urine-Sediment (microscopic examination, only if urine analysis abnormal)	Urine Sediment Bacteria Urine Cast in Sediment Urine Squamous Epithelial Cells Urine Sed. Crys., Unspecified Urine Sediment RBC/ Erythrocytes Urine Sediment WBC/ Leucocytes
Urine (only at Visit 1)	Albumin (quantitative)
Interferon Gamma Release Assay (IGRA)	QuantiFERON®-TB or T-spot at EoT visit ^{2,3}

1. Only in case of allergic reaction
2. Patients with indeterminate QuantiFERON or invalid/borderline T-spot may be retested with IGRA (once) and if inconclusive should have a PPD skin test. .
3. In subjects with a negative QuantiFERON®-TB-Gold Plus or PPD skin test, the test should be repeated every 52 weeks (including the test at the EoT visit) as long as the results are negative.
4. Creatinine can be measured by any of the three serum creatinine assays listed in the table below:

Short name	Name of serum creatinine assay	Substrate	Other information
CREE	Creatinine, enzymatic	creatinine	Enzymatic
CREJIDMS	Creatinine, Jaffe, IDMS	creatinine	Jaffe reaction, IDMS standardized
CREJ	Creatinine, Jaffe, Not IDMS	creatinine	Jaffe reaction, Not IDMS standardized

